5.4 Genome-wide association studies

5.4.1 Pre-processing

For pre-processing (QC and genotype calls) the Illumina chips, we will use the commercial program Bead Studio developed by Illumina. Although, Illumina does not provide a Linux port of Bead Studio, one can run the software on VMWARE running on a Linux host. A two CPU dual core (four cores) AMD Opteron Socket F workstation with 16GB of RAM

will be available for this purpose (the statistical analyses will be carried out on a Linux server with four quad-core Opteron CPUs (16 cores) with 64GB of RAM [expandable to 128GB if needed]).

5.4.2 Analyses to assess genotyping quality and population stratification

Initial quality studies will be conducted to identify SNPs that have generated sufficiently poor quality genotype data and should be removed from analyses. Call rate, patterns of missing data, and departures from Hardy-Weinberg equilibrium (HWE) assessed using an exact test will all be scrutinized to identify markers that will not be used in analysis. In general, SNPs with call rates <95% and those with highly significant departures from HWE ($p < 10^{-7}$) will not be included in analyses. Non-random patterns of missing data are sometimes encountered in data generated on high-throughput genotyping platforms; the most common non-random missing data problem is that heterozygous genotypes are more likely to be assigned as missing than either homozygous genotype. We will perform analyses using blind duplicates as well as analyses assessing the relationship between heterozygous call rates and missing data to identify any SNPs in which data are clearly not missing at random. Depending on the number and degree of difficulty observed, we will either remove problematic SNPs from analysis, or assign quality scores to reflect the extent of the non-random missing data.

Additional preliminary quality control analyses will be conducted to ensure that the sample does not include duplicated samples or closely related individuals. These analyses can be rapidly conducted using PLINK.³⁰⁰ Duplicated samples (or unrecognized identical twins) will be reduced to a single sample for further analyses. Although we do not expect to have closely related individuals included in this sample, only one member of any set of first-degree relatives will be included in subsequent analysis.

Population structure that is not appropriately recognized and accommodated can lead to both false positive and false negative results in association studies. We will conduct studies using structure³⁰¹ to estimate ancestry proportions using 10,000 SNPs chosen for having no pairwise LD with unrelated individuals from the HapMap CEU, YRI and CHB+JPT samples used to model the ancestral populations. Substantial previous research has shown this to be a rapid and effective approach to defining historical geographic ancestry. Although self-identified race/ethnicity is usually highly correlated with estimated historical geographic ancestry, there are often a few individuals who appear to be misclassified with self-defined labels, and it is the genetically defined ancestry that is critical to correctly accommodate to ensure robust results from association studies. Each individual will then have estimates of European, African and Asian ancestry. For individuals with high ancestry proportion for a single group (>98%), we will conduct further analyses with eigenstrat³⁰² using all SNPs to determine whether there are additional important sources of variation among individuals leading to detectable stratification by allele frequencies (reflecting, for example, differences in ethnic make-up within individuals of European descent from different U.S. cities from which subjects for the trial were obtained). Primary analyses, described below, will be conducted within groups defined by historical geographic ancestry. Secondary analyses will be conducted using logistic regression with ancestry proportions (and any additional stratification identified using eigenstrat) as covariates.

5.4.3 Feature discovery

The association between the genotype call (say AA, AB or BB) for each autosomal SNP and the clinical outcome [for example, adverse event (AE) or no AE] will be investigated within the framework of 2 by 3 contingency table stratified by ancestry. Fisher's exact test (i.e., randomized conditional counterpart to Fisher's test for 2 x 3 tables)³⁰³ will be used for carrying out inference on these tables. A feature (SNP) will be considered significant if the

corresponding nominal unadjusted two-sided P-value is less than $0.05/K$, where K is number of features which pass the pre-processing step. Needless to say, this approach may be conservative. It does however guarantee strict type I error control.

For the sake of discussion, let B denote the risk allele with an assumed relative allelic frequency of q . Under the Hardy-Weinberg equilibrium assumption, the genotypes AA , AB or BB will have relative genotypic frequencies of $(1-q)^2$, $2q(1-q)$ and q^2 , respectively. Let D denote the binary clinical outcome ($D=1$ if the AE event occurs or $=0$ otherwise) and define the probability of an AE occurrence given the copies of the risk allele on the genotype, to be denoted by G , as $p_g = P[D=1|G=g]$, for $g=0,1$ or 2 . The relationship between the event probability $p = P[D=1]$ in the general population is then expressible as the following mixture $p = (1-q)^2 p_0 + 2q(1-q)p_1 + q^2 p_2$. The effect size in the context of genome-wide association studies is typically quantified using the genotype relative risk (GRR) whose definition depends on the disease model. Under the recessive disease model, $p_0 = p_1$ and $p_2 = GRR p_0$ while under the dominant disease model $p_1 = p_2 = GRR p_0$. Finally, under the multiplicative (log-additive model), $GRR = p_1/p_0 = p_2/p_1$. Under these disease model, the event probability in the population, p , can then be reformulated as the mixture $p = (1-q)^2 p_0 w_0 + 2q(1-q)p_0 w_1 + q^2 p_0 w_2$, where $w = (w_0, w_1, w_2) = (1, 1, GRR)$, for the recessive model, $w = (1, GRR, GRR)$ for the dominant model and $w = (1, GRR, GRR^2)$ for the multiplicative model.

The clinical study plans to contribute 2,500 patients to this intergroup study. It is assumed that 85% of these patients will provide consent and usable samples for this companion study. The analysis population will consist of those self-reported as Caucasian on the CRF form. The expected proportion for this population is at least 0.85. The companion study will be powered based on a sample size of 1806 ($=2500 * 0.85 * 0.85$). The power, at the two-sided 0.05/600000 level (i.e., assume $K=600,000$ autosomal SNP markers pass through the pre-processing step) is 0.9, for a range of relative allele frequencies (q) assuming the event probability is $P[D=1]=0.3$ under recessive, dominant and multiplicative models assuming HWE.

5.4.4 Submission of molecular data

The laboratory of [name] will submit the Illumina *.idat image files using secure means to the Alliance Statistics and Data Center at Duke University. The lab will also submit a table along with this transmission, which at the minimum will provide the following information for each sample received from the repository.

The lab ID number provided by the repository.

The experimental ID, a concatenation of the plate, well and replicate information, generated by the lab.

The idat file names (the file string name will contain the Lab ID).

The md5sum signature of the idat files to ensure data integrity.

The date the specimen was received from the repository.

The date the sample was analyzed by the RIKEN laboratory.

Additionally, the lab will also provide the complete results from any quality control measures carried out. If a sample had to be redone (e.g., defective or poor quality array), the lab will provide all replicate idat files and add an appropriate column to the supplementary table. The molecular data generated for this aim may not be shared with other investigators or used for any analysis not specified in the protocol until a formal approval from the Alliance Statistics and Data Center at Duke University is obtained.

5.4.5 Secondary objectives

Logistic regression models and conditional inference trees (or more generally conditional random forests) will be used to construct multi-variable models based on the SNPs identified as interesting. These models also allow for inclusion of other potentially relevant clinical and demographic variables.

The Illumina Human610 Quad chip contains 184,064 SNPs in regions with common copy number variants (CNVs). Given the complex structure of CNVs, it is not always clear how to define the genotype of a CNV. Instead of categorizing copy numbers into genotypes, we will estimate relative genomic abundance probe intensities. This approach allows for the consideration of other CNVs beyond deletions, including duplications and combinations of both. For notational brevity, we shall refer to these as CNV markers.

For each objective, the association between each CNV marker and the clinical AE endpoint, will be assessed using the Wilcoxon two-sample test. The family-wise error rate will be controlled at the 0.05 level using permutation resampling (based on B=100,000 replicates).

Regression methods, as in the case of the SNP markers, will be employed to construct multivariable models based on the CNV markers.

Secondary relevant clinical endpoints include other adverse events (e.g., proteinuria and hypertension), progression-free and overall survival. For censored time-to-event outcomes, the stratified log-rank test will be primarily used for assessment of significance.

A risk analysis will be carried out by comparing the genotypic distributions of the SNPs from the CALGB/SWOG C80702 data to those from controls (thought to not to have cancer). The SNP data from the controls will be obtained from public databases.

In addition to conducting analyses on all features directly assessed on the high-throughput platform used in these studies, we will also interrogate all additional HapMap SNPs that are not in strong pairwise LD with any genotyped SNP but for which there is sufficient multi-locus LD to SNPs on the high-throughput platform. TUNA (Testing UNtyped Alleles) is a robust approach for conducting such analyses that provides inexpensive in silico follow up to the initial analysis and allows us to more efficiently design any follow up genotyping studies.^{304,305} For example, use of Illumina HumanHap300 enables direct testing of 270K-450K SNPs, and indirect testing of 750K-1.5M additional SNPs (i.e., these SNPs are so highly correlated with SNPs that are directly tested for association that testing them would provide little additional information). The ranges given above bracket the expectations for different human populations, with European populations at the high end of the range, and populations of recent African descent at the lower end. Use of TUNA enables interrogation of an additional 100K-250K SNPs that are neither on the platform nor highly correlated with any individual SNP on the platform. Note that use of TUNA will facilitate comparisons to genome-wide association studies on potentially related phenotypes (e.g. clinical trials of the same or related drugs) conducted using other high-throughput platforms or candidate gene studies utilizing SNPs not directly genotyped on the high-throughput platform chosen for our studies.

Finally, we note that the methodology field for the analysis of genome-wide SNP data is in its infancy. We will consider the employment of “newer” methods if they are deemed to be statistically sound and enable us to better interrogate, and more importantly, understand the data.

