2.4 Genome-wide association studies

Most pharmacogenetic analyses have taken a candidate gene approach that utilizes biological data to guide the selection of drug response genes in a pathway. This approach is limited by our knowledge of the mechanisms underlying the phenotypes. In the case of drug response phenotypes, most candidate gene studies have focused on drug metabolizing enzymes and transporters, thus limiting the chance of discovering causal SNPs not involved in mediating drug levels.^{227,228} In contrast, a genome-wide approach collects SNP data across the entire human genome and has significant power to detect common variants that confer a modest risk for a complex phenotype.²²⁹ Genome-wide studies capitalize on the large number of SNPs (more than 10 million available in dbSNP) that have been localized and validated across the genome, a majority of which have resulted from the HapMap project.²³⁰ This valuable collection of publicly available, validated SNPs has provided the framework for performing genome-wide association studies. Recent technological advancements in genotyping platforms have also enabled the development of genome-wide associations. Searching the whole genome in an association study requires genotyping of anywhere between 10^5 to 10^6 markers across the genome.²³¹⁻²³⁴ Until recently, this approach was fiscally prohibitive and impractical. However, new gene chip platforms from Affymetrix and Illumina have made large-scale genotyping feasible and cost effective. The Illumina Infinium OmniExpress chip that will be used in this study has the capacity to genotype over 555,000 SNPs simultaneously. In addition, there are 4,300 SNPs in regions of copy number variations (CNVs), thus allowing for the detection of CNVs as well. This new capability represents a paradigm shift in the number of genotypes that can be evaluated in any given individual with one genotyping assay and provides a platform for the identification of novel genes involved in the response to and toxicity associated with 5-fluorouracil, oxaliplatin, and celecoxib.

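### The copy-number test in Appendix III, 5.4.5 names no plate or ancestry strata and no permutation blocks, so its 0.05 family-wise level rests on unstated conditions and power may be lost

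*Combined protocol and SAP*

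**What the plan says.** Appendix III, 5.4.5 (Secondary objectives) sets out the copy-number (CNV) analysis separately from the SNP analysis.

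- **Measurement:** "Instead of categorizing copy numbers into genotypes, we will estimate relative genomic abundance probe intensities". The marker is therefore continuous, not a genotype call.
- **Test:** "the association between each CNV marker and the clinical AE endpoint, will be assessed using the Wilcoxon two-sample test".
- **Error control:** "The family-wise error rate will be controlled at the 0.05 level using permutation resampling (based on B=100,000 replicates". How the labels are permuted is not stated.
- **Later modelling:** multivariable regression on the CNV markers is to follow the SNP approach.

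Other sections bear on this test.

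- **Ancestry, 5.4.2:** "Population structure that is not appropriately recognized and accommodated can lead to both false positive and false negative results in association studies". The section estimates ancestry with structure and eigenstrat. Primary analyses are run within ancestry groups, and secondary analyses use logistic regression with ancestry covariates.
- **SNP test, 5.4.3:** a contingency-table test that is explicitly stratified by ancestry.
- **Population, 5.4.3:** "The analysis population will consist of those self-reported as Caucasian on the CRF form", giving n=1806.
- **Plate, 5.4.4:** the laboratory sends, for each sample, "The experimental ID, a concatenation of the plate, well and replicate information". No section uses plate as a stratum, covariate or permutation block, and none describes balancing samples across plates.

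**The concern.** A two-sample Wilcoxon test with outcome labels permuted across all patients controls error only if patients are exchangeable across whatever else moves the intensity. Two such factors are in view. Ancestry is one the plan itself warns about. Plate is a natural one for a continuous intensity, and the plan collects it.

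Two consequences follow. If both intensity and AE rate differ between plates or between residual ancestry groups, a marker with no effect can be declared associated with neuropathy or another toxicity, and the family-wise adjustment does not prevent it. If intensity differs by plate and the AE rate does not, the level is safe, but plate noise enters the comparison and real effects are harder to find.

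The 5.4.2 rule does not settle the matter. The CNV test sits under secondary objectives, for which that rule prescribes logistic regression, but the test named is a Wilcoxon test and cannot take covariates. The later regression models are not the marker-level test that carries the 0.05 family-wise claim.

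**Working it through.** **The plan's own figure.** Sample size: 2500 × 0.85 × 0.85 = 1806.25, stated as 1806. It reproduces. The CNV test has no stated power. The AE probability of 0.3 is from 5.4.3.

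**Residual ancestry (assumed inputs).** Let a share f of the 1806 have differing ancestry, with AE rate 0.40 against 0.30 and mean intensity shifted by d within-group SDs. The marker has no true effect.

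- Case and control shares: a1 = 0.40f/p and a0 = 0.60f/(1−p), with p = 0.40f + 0.30(1−f).
- P(X1>X0) − 0.5 = (a1 − a0)(Φ(d/√2) − 0.5).
- Mean Z = that quantity / √[(n+1)/(12·n1·n0)].

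For f = 0.05 and d = 2: p = 0.305, n1 = 550.8, n0 = 1255.2, a1 = 0.0656, a0 = 0.0432. The difference is 0.0224 × 0.4214 = 0.00944, the standard error is 0.01476, and Z = 0.64. The two-sided threshold 0.05/184,064 = 2.7e-7 has critical value 5.14. The rejection probability is 3.4e-6, a factor of about 12.

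| f | d | mean Z | rejection at 0.05 | factor at 0.05/184,064 |
|---|---|---|---|---|
| 2% | 1 | 0.16 | 0.053 | 1.4 |
| 2% | 2 | 0.26 | 0.058 | 2.1 |
| 5% | 1 | 0.40 | 0.068 | 3.9 |
| 5% | 2 | 0.64 | 0.098 | 12 |

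With equal AE rates the factor is 1. The size of the marker family is itself unclear. Section 5.4.5 says "The Illumina Human610 Quad chip contains 184,064 SNPs in regions with common copy number variants (CNVs", while section 2.4, naming a different chip, says "there are 4,300 SNPs in regions of copy number variations (CNVs), thus allowing for the detection of CNVs as well". At 0.05/4,300 the same Z values give factors of about 1.3 to 7.8.

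**Plate and error rate (assumed inputs).** Take 19 plates, so m = 1806/19 = 95 patients each. Let plate means have SD s in within-plate units, and let the AE rate vary between plates with SD a around π = 0.3. Approximately,

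Var(Z) = 1 + m·a²·s² / [π(1−π)(1+s²)].

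- s = 0.5, a = 0.03: 1 + 95 × 0.0009 × 0.25/0.2625 = 1.08
- s = 0.5, a = 0.05: 1.23
- s = 1.0, a = 0.03: 1.20
- s = 1.0, a = 0.05: 1 + 95 × 0.0025/0.42 = 1.57

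Simulation at these settings (1,500 runs each) gave 1.05 to 1.46 for the plain test and 0.93 to 1.00 for the plate-stratified test. If either a or s is zero, the excess vanishes.

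**Family-wise error.** A max-statistic permutation procedure was simulated with n=1806, 200 null markers, 200 permutations and 400 replicates (Monte Carlo SE about 0.011).

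| Setting | labels permuted freely | within block |
|---|---|---|
| Plate: no differences | 0.035 | 0.038 |
| Plate: AE rate constant, s = 0.5 | 0.070 | 0.050 |
| Plate: AE log-odds SD 0.2, s = 0.25 | 0.075 | 0.045 |
| Plate: AE log-odds SD 0.2, s = 0.5 | 0.118 | 0.065 |
| Plate: AE log-odds SD 0.4, s = 0.5 | 0.468 | 0.060 |
| Ancestry: 5% share, AE 0.40 vs 0.30, group-shift SD 0.5 | 0.078 | 0.055 |
| Ancestry: 5% share, AE 0.40 vs 0.30, group-shift SD 1 | 0.115 | 0.045 |

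A log-odds SD of 0.2 is about 0.2 × 0.21 = 4 percentage points, and 0.4 is about 8, so the 0.468 row lies beyond the 3-5 point range used above. Results for 184,064 markers would differ.

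**Plate and power.** With no link between plate and AE, plate variation raises the noise SD by √(1+s²), an efficiency of 1/(1+s²): 80% at s = 0.5 and 50% at s = 1. Take an effect with stratified power 0.81 at two-sided 0.05, a noncentrality of 1.96 + 0.88 = 2.84. The plain test has 2.84/1.118 = 2.54 (power 0.72) or 2.84/1.414 = 2.01 (power 0.52). Simulation gave 0.72 and 0.54. Without plate effects the stratified test lost essentially nothing.

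**The case against.** The strongest reply is that ancestry is handled. Section 5.4.2 states a general rule above 5.4.5, 5.4.3 limits the population to self-reported Caucasians, and 5.4.6 mentions logistic regression with ancestry covariates. This largely stands. A reader might infer that the plan ignores ancestry, and the documents do not support that. What remains is that the rule is not translated into a Wilcoxon test, and that 5.4.2 itself says self-reported labels misclassify a few individuals and that structure can exist within European descent.

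A reader might also apply the whole-trial mix: 283/2500 = 11.3% Black or African American and 2500 × 0.85 = 2,125 samples, which gives inflation of 41 to about 420 times. That is not the planned analysis population, and those figures do not describe this test.

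A reader might take it that labels are permuted freely over the whole sample. That is the default reading, but the plan does not specify the scheme.

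On plate, no section says the intensities depend on plate or that the AE rate differs by plate. Section 5.4.1 provides for pre-processing and 5.4.4 requires quality-control results. This stands against any claim that bias is present. It does not rule bias out. Accrual was expected to span 6/2010 to 6/2015 (Appendix VI), protocol 5.8.5 allows blood to be drawn at any time on study, and Appendix II, 4.1 guards against batch effects for the microbiome assays. The power loss needs no link between plate and AE.

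**Conclusion.** The gap is real but narrow. The marker-level CNV test is written without strata or permutation blocks. Recorded plate is unused, and the existing ancestry rule is not carried into this test. The stated 0.05 family-wise level then depends on intensity and AE rate not both varying by plate or residual ancestry, which the documents neither show nor exclude.

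Every size rests on assumed differences. For residual ancestry of 2-5% in the planned population the inflation is about 1.4- to 12-fold at 0.05/184,064. For plates the variance of Z runs from about 1.0 to 1.6 unstratified, against about 1.0 stratified. The clearest gain is in power if plate shifts are 0.5-1.0 SD. CNVs appear in objectives 1.4 and 1.5 of an optional companion study, so the point is minor and leaves the trial's DFS result untouched.

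**What to change.** State in 5.4.5 that, within the ancestry group already defined in 5.4.2, each CNV marker will be tested by a plate-stratified (van Elteren) Wilcoxon test, and that AE labels will be permuted only within plate to obtain the family-wise p-values. Handle residual or admixed ancestry by first regressing the intensity on the ancestry proportions and eigenstrat axes, then ranking the residuals.

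Full ancestry-by-plate strata are not advisable. With a 5% share, a plate of 95 would hold about 95 × 0.05 = 4.8 such patients and one or two events, and admixed patients would have no stratum.

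The cost is a sentence or two, since plate and ancestry estimates are already to be available. At an AE rate of 0.3 a plate holds about 28 events, so little information is lost. Plates with very few events contribute little, which matters mainly for rare AEs. The same edit should reconcile the chip and the number of CNV markers between 2.4 and 5.4.5.

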5.4.6 Statistical software

The R statistical environment³⁰⁶ and Bioconductor³⁰⁷ packages will be used for all of the primary statistical analyses relating features to phenotypes. Specialized statistical genetics software, including PLINK,³⁰⁰ structure,³⁰¹ eigenstrat,³⁰² and TUNA^{304,305} will be used for some of the quality or secondary analyses, and R will be used for logistic regression analyses allowing for ancestry covariates.

